**Most recent IRB continuation approval: 10/30/2018**

# PROTOCOL AND STATISTICAL ANALYSIS PLAN

## Specific Aim and Hypotheses

To evaluate the impact of a 3-part decision aid (DA) intervention of an individualized decision-aid (1), provider education (2), and modified performance measure/reminder (3) versus a pragmatic control (PC) that includes provider education and modified performance measure/reminder, but no decision aid, on the frequency of CRC screening orders in a cluster-randomized controlled trial.

*H1a: Individuals in the DA group will receive screening orders less often than those in the PC group.*

*H1b: Individuals in the DA group will receive screening orders that are more concordant with screening benefit than those in the PC group.*

## Research Design and Methods

The 30-month, 3-part intervention is directed at patient-, provider-, and system-level factors. First, we provided patients with a personalized decision aid (intervention component 1 of 3) that worked to educate Veterans about the underlying reasons for screening and informed them about the risks and benefits (tailored to demographic characteristics and comorbidity burden), thereby enhancing their conceptual understanding and increasing the accuracy of their perceptions about CRC and screening. The decision aid also included a values-clarification exercise to help them clarify their personal values and preferences regarding screening. Second, we educated providers (intervention component 2 of 3) to increase their general knowledge of the underlying data on screening in elderly individuals. Individualized risk information from the decision aid was also available to providers, enhancing their knowledge of the risks and benefits of screening specific to their patients. Finally, we addressed system-level factors by modifying performance measurement and clinical reminder (performance management) systems to ease institutional pressures on providers to order screening without discussing risks and benefits (intervention component 3 of 3).

## Patient Recruitment

We identified Veterans who were scheduled for a primary care visit 4 weeks from the recruitment date and met the following inclusion criteria: age 70-75 and due for CRC screening according to the 2008 USPSTF guideline (using Logical Observation Identifiers Names and Codes (LOINC) to identify FOBT in the last 12 months and Current Procedural Terminology (CPT) codes to identify colonoscopy in the last 10 years, as well as data from the clinical reminder system). The medical records of these potential participants were then manually reviewed by the research assistant to confirm eligibility. Individuals with limited life expectancy (documented electronically under "Health Factors"), or for whom the medical record indicates provider intention to not screen due to health problems, will be excluded. Veterans whose eligibility was confirmed were mailed an invitation along with a return postcard. This invitation will briefly outline the purpose and nature of the study and ask the participant to call a toll-free number and leave a message if they are not interested in participating. If no "opt out" response is received after 1 week, the Veteran was contacted via telephone by the research assistant to confirm eligibility and a desire to participate. Interested Veterans were asked to arrive at the clinic 1 hour prior to their scheduled appointment to provide informed consent, complete survey instruments, and review the decision aid materials, if primary care provider was randomized to the decision aid, or review a brief CRC screening control booklet.

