## Study Visit Procedure

Providers who consented to participation in the study were randomized to the intervention or control arm of the study (1:1 FTE randomization). Veterans who consented to participate were asked to complete a survey ("pre-visit survey") on the day of the clinic visit to collect relevant baseline data. Participants then received the decision aid or control booklet (based on the randomization of their provider). Those who received the decision

aid were asked to review the materials just prior to the clinic visit, with the help of the research assistant. The participant then proceeded with the scheduled clinic visit. A second survey (“post-visit survey”) was administered immediately after the clinic visit, to collect data on informed decision making and conceptual understanding of screening. Participants received a \$40 gift card for participating in the study. We used manual record review of EHRs to determine whether screening was ordered at the visit (gave 2 weeks for the order to appear in patients’ medical records) and whether screening was utilized at 6 months.

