## Secondary Outcome Measures

Expected benefit of screening (H1b): We hypothesized that Veterans randomized to the DA intervention (who will have received individualized benefit and risk information in the decision aid) will receive screening orders that are more concordant with screening benefit than those randomized to the pragmatic control (H1b). The expected benefit of screening (reduction in CRC mortality) will be calculated using the MISCAN-Colon model. For a given patient, this value will be a function of age, gender, ethnicity, health status, and prior screening history, all of which were obtained from CDW and the pre-visit survey.

Screening utilization: We determined whether screening was utilized within 6 months of the clinic visit from CDW data using an electronic algorithm that we previously developed for a study of CRC screening overuse; utilization was confirmed through manual record review.

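### No health-adjusted H1a analysis is stated, although enrolment depends partly on a chart judgement that may be made with the provider's arm known

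*Combined protocol and SAP*

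**What the plan says.** All references are to the Combined protocol and SAP.

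- **Exclusion.** Patient Recruitment says that Veterans "for whom the medical record indicates provider intention to not screen due to health problems, will be excluded". Limited life expectancy, the other health-based exclusion, has an electronic field; no field is named for provider intention. Table 1 lists the life-expectancy criterion but not this one.
- **Who applies it.** "The medical records of these potential participants were then manually reviewed by the research assistant to confirm eligibility". Later, "the Veteran was contacted via telephone by the research assistant to confirm eligibility and a desire to participate".
- **Who helps with the aid.** In Study Visit Procedure, those who received the decision "aid were asked to review the materials just prior to the clinic visit, with the help of the research assistant".
- **When.** Patients are found when "scheduled for a primary care visit 4 weeks from the recruitment date". Their arm follows the provider: "Participants then received the decision aid or control booklet (based on the randomization of their provider").
- **H1a model.** Data Analysis gives a logistic mixed model with study arm as the primary independent variable and provider random intercepts. No other covariate is named. Expected benefit and its interaction with arm enter only for H1b.
- **Data in hand.** Secondary Outcome Measures derives expected benefit from "age, gender, ethnicity, health status, and prior screening history, all of which were obtained from CDW and the pre-visit survey".

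**The concern.** In a cluster trial, patients selected after their cluster is allocated, by staff who may know the allocation, can differ between arms even though the clusters were randomised fairly. Here the selection rule is a judgement about whether the provider means to screen, which is close to the outcome itself. Someone who helps with the aid must know which patients are in the decision-aid (DA) arm, and once a provider is randomised the provider's name reveals the arm.

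If more poor-health patients were excluded from the DA arm, its order rate would rise and the H1a difference would shrink. If more were excluded from the pragmatic control (PC) arm, the difference would be inflated, or a false one created. The provider random intercept models correlation within providers; it does not remove a systematic difference in health between arms.

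**Working it through.** **1. The plan's own figure.** Inputs from Sample Size Calculation: 50% v 35%, 40 providers, ICC 0.02, two-sided 0.05. Effective n per arm = (N/2)/(1 + (m − 1) × ICC), with m = N/40.
- N = 440: m = 11, design effect 1.20, effective n 183.3. SE = √((0.25 + 0.2275)/183.3) = 0.0510, and 0.15/0.0510 = 2.94. With 38 df, power is 81.7%, so 440 is reproduced.
- N = 600: m = 15, design effect 1.28, power 89.9%.

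The sample size is not in question.

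**2. Timing.** Assume even accrual, and each provider randomised no later than the first participant's visit. Only reviews in the 4 weeks before that visit can then precede randomisation: 4/104 weeks = 3.8% over the planned 24 months, 4/52 = 7.7% if a provider recruits for 12 months, 4/26 = 15% for 6 months.

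**3. Size of a shift.** The documents give no exclusion rate and no order rate by health, so these inputs are assumptions: 25% in poor health; PC order rates in poor/good health of 20%/60% (strong link) or 35%/55% (weak link). Each gives 50% overall: 0.25 × 0.20 + 0.75 × 0.60 and 0.25 × 0.35 + 0.75 × 0.55. One odds ratio per case brings the DA arm to 35%: 0.502 (11.1%/43.0%) or 0.529 (22.2%/39.3%).

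If a share x of one arm is excluded in excess, with order rate q among them, that arm's rate becomes (p − xq)/(1 − x). With all of x in poor health, x = 5% or 10% means that the arm loses 0.05/0.25 = 20% or 0.10/0.25 = 40% of its poor-health patients.

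- DA excess 10%, strong: (0.35 − 0.10 × 0.111)/0.90 = 37.7%; 15 points becomes 12.3.
- DA excess 5%, weak: (0.35 − 0.05 × 0.222)/0.95 = 35.7%; 15 becomes 14.3.
- No true effect, PC excess 10%, strong: (0.50 − 0.10 × 0.20)/0.90 = 53.3%; false difference 3.3. Weak: (0.50 − 0.10 × 0.35)/0.90 = 51.7%; 1.7.
- The same, but excluded patients have a 5% order rate: (0.50 − 0.10 × 0.05)/0.90 = 55.0%; 5.0.

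The shifts run from 0.7 to 5.0 points.

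**4. What adjustment does.** Simulation: 40 providers × 15 patients, random-intercept variance 0.08 (about ICC 0.02), 2,000 trials per case, Wald test at 0.05.

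| Case | Unadjusted | Adjusted |
|---|---|---|
| No excess, power, strong | 92.6% | 94.5% |
| No excess, power, weak | 91.9% | 92.5% |
| No excess, error, strong / weak | 5.9% / 5.8% | 5.8% / 5.4% |
| DA excess 10%, strong | 12.3 points, power 79% | 15.3 points, 94% |
| DA excess 10%, weak | 13.5 points, 86% | 15.0 points, 92% |
| Null, PC excess 10%, strong | 3.4 points, error 11.6% | 0.1 points, 5.9% |
| Null, PC excess 10%, weak | 1.7 points, error 7.7% | 0.1 points, 5.9% |
| Null, PC excess 10%, excluded order rate 5%, strong | 5.1 points, error 21.4% | 2.1 points, 7.7% |
| The same, weak | 5.0 points, error 20.2% | 4.1 points, 14.7% |

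The Monte Carlo standard error of a power near 92.6% is √(0.926 × 0.074/2,000) = 0.6 points. The weak-link power gain is of that size and is best read as no loss.

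Hand check of the last row: the remaining poor-health PC rate is (0.0875 − 0.005)/0.15 = 0.55, against 0.35 in the DA arm. The pooled poor-health share is (0.25 + 0.15/0.90)/2 = 0.208, and 0.20 × 0.208 = 4.2 points, against 4.1 simulated.

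**The case against.** **The planned H1b model already holds the adjustment.** It has the same outcome and random intercept, and expected benefit is built from age, health status and screening history. Its arm coefficient refers to zero expected benefit, but that is only coding. Standardising a model with the interaction, for the strong link with 10% DA excess, gives 0.208 × (0.200 − 0.111) + 0.792 × (0.600 − 0.430) = 15.3 points, the same as the adjusted result above. This stands. What remains is that the plan does not state this contrast.

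**The inputs are severe.** Losing 20 to 40% of one arm's poor-health patients is a large imbalance, and nothing in the documents suggests its size or direction. At 2% excess the false difference under the strong link is (0.50 − 0.02 × 0.20)/0.98 − 0.50 = 0.6 points. This stands; the figures illustrate and do not predict.

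**Adjustment looks best where it matters least.** In most rows the adjusted marker is exactly what drives selection, measured without error. Patients whose provider does not intend to screen should have a low order rate, and there the weak-link correction is only 5.0 to 4.1 points. This stands as a limit on what the analysis can show.

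**Stronger readings.** A reader might infer that one person did both tasks, that reviews certainly followed randomisation, or that H1a is closed to covariates. The documents support none of these: they name a role, give no dates, and call arm the primary, not the only, independent variable.

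**Conclusion.** The point holds as a modest gap in the analysis plan. An outcome-related exclusion is judged by a role that also helps deliver the intervention, with no masking described and probably, in most cases, after the provider's randomisation. No stated H1a analysis would reveal or correct a resulting difference in health, although the covariates are collected.

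A reader might go further and conclude that H1a is biased. The documents do not support that: they do not show that exclusions differed by arm, and direction and size are unknown. Under the assumed inputs, excess exclusion of 5 to 10% of one arm, all in poor health, shifts the unadjusted difference by roughly 1 to 5 points, in either direction. Without excess exclusion, adjustment costs no power and may add a little.

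Nor would an adjusted estimate that matches the unadjusted one prove that there was no bias, because selection through unmeasured factors would remain.

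**What to change.** Add to the SAP a named covariate-adjusted H1a analysis: study arm plus age, health status and prior screening history as fixed effects, with the provider random intercept kept. The planned expected-benefit value may replace the three covariates. Use only values recorded before the visit, from CDW or from the pre-visit survey, which is completed before the aid or booklet is handed over.

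Report it beside the current model, both as standardised risk differences, since adjusted and unadjusted odds ratios differ even without bias. If the team prefers to standardise the H1b model over the pooled sample, the SAP should say so. State that the analysis addresses only measured health. Report exclusions by reason and arm if counts were kept.

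The cost is one extra model, or one extra contrast, on data already obtained. Eligibility and the current H1a model do not change. Much of the text is in the past tense; if the H1a result has been seen, label the analysis post hoc.

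I would not ask for a masked second chart reviewer: it needs extra staff and would not reach chart entries written by unmasked providers.

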## Study Visit Procedure

Providers who consented to participation in the study were randomized to the intervention or control arm of the study (1:1 FTE randomization). Veterans who consented to participate were asked to complete a survey ("pre-visit survey") on the day of the clinic visit to collect relevant baseline data. Participants then received the decision aid or control booklet (based on the randomization of their provider). Those who received the decision

aid were asked to review the materials just prior to the clinic visit, with the help of the research assistant. The participant then proceeded with the scheduled clinic visit. A second survey (“post-visit survey”) was administered immediately after the clinic visit, to collect data on informed decision making and conceptual understanding of screening. Participants received a \$40 gift card for participating in the study. We used manual record review of EHRs to determine whether screening was ordered at the visit (gave 2 weeks for the order to appear in patients’ medical records) and whether screening was utilized at 6 months.

## Research Specifications

**Table 1: Design of Pragmatic Cluster-Randomized Trial**

Design	Cluster-randomized controlled trial (RCT) 1:1 provider (Full Time Equivalent or FTE) randomization
Setting	VA Ann Arbor Medical Center and its largest CBOC (Toledo), both of which are under the jurisdiction of VAAAHS leadership and a single IRB.
Study Population	
Veterans aged 70-75 who meet the following criteria:
 
 
1) Average risk for CRC
 
2) Due for screening according to the 2008 USPSTF CRC screening guideline
 
3) No documentation of limited life expectancy
 

Veteran-Centered Intervention (VC) (3 components)	
 
1) CRC screening decision aid
 
2) Provider training and education
 
3) Modified CRC screening performance management system 
 
a. Modified clinical reminder
 
b. Modified performance measure
 
c. Modified provider feedback and performance pay
 
 
 

Pragmatic Control (PC) (3 components)	
 
1) No CRC screening decision aid
 
2) Provider training and education
 
3) Modified CRC screening performance management system 
 
a. Modified clinical reminder
 
b. Modified performance measure
 
c. Modified provider feedback and performance pay
 
 
 

Outcomes	
 
1) Proportion of primary care clinic visits where CRC screening is ordered (H1a)
 
2) Benefit-concordance of screening orders (H1b)
 
3) Screening tests completed (utilization) (H1c)
 

## Primary Outcome Measure

**CRC screening orders (H1a):** We hypothesized that Veterans randomized to the DA intervention would receive fewer screening orders than those randomized to the pragmatic control (H1a). Thus, the primary dependent variable in our analysis was whether screening was ordered at the clinic visit (dichotomous; gave 2 weeks for the order to appear in patients’ medical records)). We then determined whether screening was ordered through manual record review.

## Secondary Outcome Measures

Expected benefit of screening (H1b): We hypothesized that Veterans randomized to the DA intervention (who will have received individualized benefit and risk information in the decision aid) will receive screening orders that are more concordant with screening benefit than those randomized to the pragmatic control (H1b). The expected benefit of screening (reduction in CRC mortality) will be calculated using the MISCAN-Colon model. For a given patient, this value will be a function of age, gender, ethnicity, health status, and prior screening history, all of which were obtained from CDW and the pre-visit survey.

Screening utilization: We determined whether screening was utilized within 6 months of the clinic visit from CDW data using an electronic algorithm that we previously developed for a study of CRC screening overuse; utilization was confirmed through manual record review.

## Data Analysis

CRC screening orders (H1a): To assess the primary outcome (CRC screening orders), we used a generalized linear mixed-effects model with logit link, using screening orders as the dependent variable. The primary independent variable was study arm. Because randomization was done at the provider level, we anticipated that patients with the same provider would show a positive intraclass correlation (ICC). The mixed-effects model will account for such clustering by including providers as random intercepts. We did not account for patient dropout since all data collection was done at the clinic visit, with the exception of ordering and completion of screening, which is collected electronically via EHR data and does not require further patient participation.

Benefit-concordance of screening orders (H1b): We examined whether the expected benefit of screening was an important factor in determining ordering of screening (H1b). This analysis followed the approach outlined above for screening orders, but we added as covariates the expected benefit of screening and an interaction term between study arm and expected benefit of screening.

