## Sample Size Calculation

**Table 2: Sample Size Calculations**  
(40 providers/clusters, ICC = 0.02, power = 0.8)

Screening Orders (Control Group)	Screening Orders (Experimental/Intervention Group)	Sample Size (Total)
50%	30%	240
	35%	440
	38%	760
	40%	200
	25%	400
	28%	680

Preliminary data demonstrate that approximately 1,200 screen-due Veterans between 70-75 years of age with comorbid illness will present to the VA Ann Arbor Medical Center and the Toledo CBOC over a 24-month period. Assuming a 50% participation rate (based on the participation rate observed in co-investigator [name]'s ongoing VA-funded CRC screening decision aid trial, which uses a similar recruitment method), we will have the capability of enrolling 600 patients over this time period. Preliminary data show that 35% of these individuals will complete a screening test within 6 months of the clinic visit. Based on this value and prior data on screening completion rates, we estimate that a screening test is ordered at approximately 50% of visits among patients who receive usual care (control event rate (CER) = 50%). Our survey data (see Preliminary Data, B.5.c) suggest that the VC intervention will reduce the CER by at least 30%, yielding an estimated experimental event rate (EER) of 35%. Study sites employ over 50 primary care providers (clusters), and we

expect that approximately 75% of these providers will choose to participate (based on an ongoing CRC screening study involving primary care providers at VAAAHS). Finally, based on preliminary data, we assumed an ICC of screening orders within provider of 0.02. Under these assumptions, a sample size of 440 patients would provide 80% power to detect a meaningful reduction in screening orders (H1a) (Table 4). Thus, with the proposed sample size of 600 patients, we will have more than 80% power to detect a meaningful difference in screening orders (H1a) between control and experimental groups (using two-tailed tests at an alpha of 0.05). We anticipate that this sample size will also be adequate to detect a difference in benefit-concordance of screening orders between study arms (H1b), since this analysis will simply require the addition of two additional terms in our regression equation.

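### The H1a model carries study arm alone; adding site and expected screening benefit as fixed covariates would be a cheap, small and optional gain in precision, not the correction of an error

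*Combined protocol and SAP*

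**What the plan says.** For H1a the Data Analysis section states that "we used a generalized linear mixed-effects model with logit link". The outcome is whether screening was ordered, providers enter as random intercepts, and "The primary independent variable was study arm". No other term is listed.

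The word primary does not by itself exclude further variables, but two other sentences support the arm-only reading. For H1b, "we added as covariates the expected benefit of screening and an interaction term between study arm and expected benefit of screening". The Sample Size Calculation section says of the same step that "this analysis will simply require the addition of two additional terms in our regression equation". Expected benefit is therefore not in the H1a model.

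Table 1 (Research Specifications) names two sites, Ann Arbor and Toledo. Secondary Outcome Measures says that the MISCAN-Colon expected benefit will be calculated from age, gender, ethnicity, health status and screening history, taken from CDW and the pre-visit survey. Under Study Visit Procedure, that survey precedes the decision aid or control booklet. Allocation is described as 1:1 by provider FTE, with no mention of stratification by site.

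**The concern.** The plan itself treats expected benefit as a candidate driver of orders, since H1b predicts that "Individuals in the DA group will receive screening orders that are more concordant with screening benefit than those in the PC group". Site is a natural source of variation between providers. A baseline variable that predicts the outcome can sharpen the arm comparison. With few randomised units, the arms can also differ by chance in their site mix, and the arm-only model does not adjust for that. Both variables can be had without new data collection, so leaving them out forgoes whatever precision they carry. What is at stake is a few points of power at most, and an estimate adjusted for chance imbalance. The validity of the primary test is not at stake.

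**Working it through.** **Inputs from the plan (Sample Size Calculation):** order rates 50% and 35%; ICC 0.02; two-sided alpha 0.05; 440 patients for 80% power; 600 patients proposed. Table 2 uses 40 providers; the text's 75% of just over 50 gives about 38.

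**The plan's own figure.** A two-proportion calculation with continuity correction gives 183 per arm, 366 in total. With design effect 1 + (N/40 - 1) x 0.02, N = 366 x (0.98 + 0.0005N), so N = 358.68 / 0.817 = 439.0. The stated 440 reproduces.

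**Arm-only power at 600.** Power = Φ[(0.15 - 1.96 x SE0) / SE1], where SE0² = 2 x 0.425 x 0.575 / n, SE1² = (0.25 + 0.2275) / n, and n is the effective number per arm.

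- 40 providers: design effect 1 + 14 x 0.02 = 1.28; n = 300 / 1.28 = 234.4; power 91.0%.
- 38 providers: design effect 1 + (15.79 - 1) x 0.02 = 1.296; n = 231.5; SE0 = 0.0459, SE1 = 0.0454; power 90.7% (89.5% with a t reference on 36 df).

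**Cost if site carries no information.** With 38 providers and allocation that ignores site, arm and site share on average 1/37 = 2.7% of their variance by chance. Then n falls to 231.5 x 36/37 = 225.3 and power to 89.9%, a loss of 0.8 points.

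**Chance imbalance in site.** If 30% of providers are at Toledo (assumed), the between-arm difference in site share has SD √(0.3 x 0.7 x 2/19) = 0.149. A site difference of 5 points in order rate (log OR about 0.2) then shifts the arm difference by an SD of about 0.7 points; one of 10 points (log OR about 0.4) shifts it by about 1.5. The standard error of the arm difference is 4.5 points.

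**Simulated effect of adjustment.** Random-intercept logistic fits: 38 providers, 19 per arm, 600 patients, total ICC 0.02 including site, 30% of providers at Toledo, allocation ignoring site, t reference on 36 df (arm only) or 35 df (adjusted), 5,000 runs each. All log odds ratios are assumptions. The standard error of each change is 0.2 to 0.4 points.

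| Predictor (log OR per SD) | Site (log OR) | Arm only | Arm + site + predictor | Change |
|---|---|---|---|---|
| 0 | 0 | 89.9% | 89.4% | -0.5 |
| 0.2 | 0 | 89.8% | 89.4% | -0.4 |
| 0.2 | 0.2 | 90.0% | 90.2% | +0.2 |
| 0.4 | 0 | 90.4% | 90.6% | +0.2 |
| 0.4 | 0.2 | 89.7% | 90.9% | +1.2 |
| 0 | 0.4 | 90.4% | 92.4% | +2.0 |
| 0.7 | 0 | 89.8% | 92.0% | +2.2 |
| 0.7 | 0.4 | 89.9% | 93.6% | +3.7 |

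A site log OR of 0.4 is generous: between-provider variance at ICC 0.02 is 0.02 x 0.25 = 0.005, and site alone would supply 0.21 x 0.0995² / 0.005 = 42% of it (about 10% at log OR 0.2). If the predictor acts mainly or only in the DA arm, as H1b supposes, the change lies between -0.1 and about +1. Under the null (predictor 0.4, site 0.2) both models reject in 4.8% of runs.

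**Second simulation.** With 40 providers of 15 patients and Wald z tests, the change was +0.4 with no prognostic value, about +1.2 in a middle case (0.35 per SD, site 0.3), +3.4 in a strong case (0.8, site 0.5) and +4.0 with a site log OR of 0.56 under unstratified allocation. Its null rejection rates were 3.8% arm-only and 5.0% adjusted, so part of those gains reflects a difference in test size. They are better read as upper figures.

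**Dropping patients with missing covariates.** Losing 10% (600 to 540) gives design effect 1.264, n = 213.6 and power 88.3%: a loss of 90.7 - 88.3 = 2.4 points.

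**The case against.** The strongest reply is that nothing is broken. Under provider randomisation, an unadjusted mixed model is a legitimate choice, holds its size and exceeds the 80% target. That stands. A reader might infer from the missing covariates that the primary analysis is invalid or underpowered; the documents and the figures above do not support that.

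A reader might also expect a dependable gain of a point or more. That is not supported either. The +1.2 is one favourable cell, and its neighbours show +0.2. The documents give no association between any covariate and orders, no site difference and no split of providers between sites. Eligibility also narrows the patient covariates: everyone is "age 70-75 and due for CRC screening according to the 2008 USPSTF guideline", and those with limited life expectancy, or "for whom the medical record indicates provider intention to not screen due to health problems", are excluded. Weak scenarios are at least as plausible as strong ones.

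Three further inferences should be resisted. Expected benefit is not already in hand; its inputs were obtained, but the value is still to be calculated. The plan does not leave a choice among adjusted H1a models open, because it plans none. And the absence of a statement on site stratification does not show that allocation ignored site.

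The past tense of the H1a paragraph suggests that the analysis may already have been run, although other sentences are in the future tense. If it has, the primary test gains no power, and only a sensitivity analysis remains.

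Finally, a main-effects model is misspecified if H1b is true. That limits the gain, as the interaction scenarios show, but the standardised risk difference keeps a clear meaning.

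**Conclusion.** The point holds as an optional improvement. H1a uses study arm and provider intercepts only, while site and the inputs to expected benefit are available at baseline. Against arm-only power of about 90% at 600 patients, adjustment is worth about -1 to 0 points with weak covariates, 0 to +1 with moderate ones, and +2 to +4 only with a strong predictor or a large site difference. This range rests on assumed prognostic strengths, an assumed 30% Toledo share and allocation that ignores site; the rates, ICC and sample size are the plan's. Adjusting for chance imbalance in site and benefit is a second, modest advantage. Confidence is medium: the reading of the model is secure, the size of the gain is not.

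**What to change.** **If outcomes by arm have not been analysed:** specify one primary H1a model, screening order on arm + site + MISCAN expected benefit (main effects), with provider random intercepts. Fill missing baseline inputs by simple imputation that uses neither arm nor outcome, so that no patient is dropped. Report a covariate-standardised risk difference beside the odds ratio. Keep the arm-only model as a sensitivity analysis and leave the arm-by-benefit interaction in H1b.

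**If they have been analysed:** keep arm-only as primary and report this one adjusted model as a labelled sensitivity analysis.

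**Cost:** SAP wording and a little programming; no new data, since H1b needs expected benefit anyway. The odds ratio becomes conditional on the covariates, a missing-covariate rule is needed, and about 0.5 to 1 point of power is lost if the covariates carry no information.
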